8.3.3. Covariates

Not applicable

8.4. Data Sources

8.4.1. Databases

All information will be capture from patient's medical chart since diagnosis until the most recent data available at study enrollment.

Screening of data in medical records will be conducted retrospectively to identify study candidates, followed by data collection from registrants in a manner consistent with each investigator's practice (with recording of data using electronic case report forms).

8.4.2. Linkage Methods

Not applicable

8.5. Study Size

As a descriptive study, sample size calculations are not applicable. The expected number of patients eligible for the study is approximately 700. An initial estimation of 15 sites across Argentina, Brazil, Chile and Colombia. The number for each disease will be estimated based on the feasibility assessment. Study size was estimated according to incidence of the diseases in Latin America and population size of each country [11]. In Latin America, the incidence varied from 0.51/100,000 to 2.0/100,000 for AML and from 0.81/100,000 to over 1.0/100,000 for ALL from 1990 until 2017 [11]. Considering all leukemia cases in 2017, global incidence trends correspond to 23.1% and 12.4% for AML and ALL, respectively. Higher trends were found in Southern Latin America, with 27.7% and 14.9% for AML and ALL, respectively. The number of sites and participants for each country are described below:

- Argentina: expected 3 sites with approximately 200 eligible patients
- Brazil: expected 4 sites with approximately 300 eligible patients
- Chile: expected 2 sites with approximately 100 eligible patients
- Colombia: expected 2 sites with approximately 100 eligible patients

8.6. Data Management

8.6.1. Statistical Software

All analyses will be conducted using SAS 9.4 or newer version or Python version 3.6.9 or newer version or a comparable statistical software package. The statistical software used will be reported at the final clinical study report.

Data management for this study will be conducted using standard IQVIA processes. The process would take into consideration any data governance imposed on the data source including any plans to handle the data outside of the institution or country of origin. IQVIA will adhere to all local and regional laws on data protection and privacy.

8.7. Data Analysis

Analyses will be descriptive in nature, as no hypothesis is being tested. Disease staging, comorbidities, demographic, clinical characteristics will be described at the date of diagnosis and/or treatment initiation for patients diagnosed with B-cell ALL R/R or AML. Treatment and clinical information will be assessed up to the most recent data available at the study enrollment. The treatments will be described in sequence according to the chronological order of administration. The duration through the number of cycles will be evaluated. Dose reduction information will also be collected. All analysis, including subgroup assessment, will be performed according to the data availability.

Continuous variables will be described as mean and standard deviation (SD), and/or as median, minimum, maximum, interquartile range (IQR, 25th and 75th percentiles). Categorical variables will be described by simple and cross contingency tabulation, with absolute frequencies and percentages. Missing values will be included in the denominators for the calculation of percentages and missing categories will be presented.

Follow-up period will be considered the time (in years) elapsed since B-cell ALL R/R or AML diagnosis until the study enrollment. It will be summarized as a continuous variable.

All time-to-event analysis will be described using Kaplan Meier methods and plots, if appropriate. The following definition and parameter analysis will be considered:

- Time to next treatment (TTNT) – considered as the time from the start date of the front-line therapy to the start date of a subsequent line of therapy. Patients without a subsequent line of therapy will be censored at study enrollment, last visit, last contact, or death, whichever comes first. It will be presented in months.
- Overall survival (OS) – considered as death from any cause from the time of initiation of diagnosis or treatment [12,13]. Patients not known to have died will be censored at study enrollment, last visit, last contact, whichever comes later. The median OS and, if feasible, the % of alive patients in 1, 3- and 5-years follow up of newly diagnosed AML and R/R B-cell ALL patients will be assessed.
- Relapse-free survival (RFS) for newly diagnosed AML patients – considered as the date of achievement of a remission until the date of relapse or death from any cause; patients not known to have relapsed or died at last follow-up are censored on the date they were last examined, study enrollment, last contact, whichever comes later. Defined only for patients achieving CR, or CRI. The RFS will be measured as the treatment end date until next treatment initiation or date of death, whichever comes first, for all AML patients who achieved Complete remission/response (CR) or Complete remission/response with incomplete hematological/count recovery (CRI) at the end of treatment.
- Event-free survival (EFS) of newly diagnosed AML and R/R B-cell ALL patients – considered as the date of initiation of treatment (or date of diagnosis, if the previous is not available) to the date of primary refractory disease, or relapse from CR, or CRI, or death from any cause; patients not known to have any of these events are censored on the date they were last examined, study enrollment, last contact, whichever comes later. The EFS will be measured as the time since AML and R/R ALL initiation of treatment (or newly AML diagnosis and newly ALL diagnosis, if treatment date is not available) until i) treatment end date (or treatment start date of the next treatment line, if the previous is not available) when treatment response was Refractory disease(5) or Relapsed from CR or CRI or recurrent disease(6) as treatment response; ii) date of death, whichever comes first.
 - Clinically relevant events:
 - Hematological toxicities
 - Hepatotoxicity
 - Gastrointestinal toxicities
 - Tumor lysis syndrome
 - Fatigue
 - Dysgeusia
 - Alopecia
 - Muscle spasms
 - Infections

- Sepsis
- Secondary malignancy due to drug toxicity
- Death
- Other

Medical Dictionary for Regulatory Activities Terminology (MedDRA) version 2.1 (V2.1) or newer version will be used as a standardised medical terminology. Medicinal product names will be codified using World Health Organisation Drug Dictionary (WHODrug), a dictionary maintained and updated by Uppsala Monitoring Centre (UMC).

The resource utilization (e.g., number of hospital admissions, hospitalization period, procedures during hospital admissions) will be presented, if possible, as mean number per patient per year (PPPY). According to the sample distribution, the data will be presented with a standard deviation (SD) or a 95% confidence interval (95% CI), which will be estimated with the most appropriate distribution, which may include Negative Binomial, Poisson or Gama distribution. The statistical distribution will be chosen with quantil-quantil plots (QQplots).

For each resource utilization, the PPPY will be calculated as the sum of all utilizations, divided by the follow up, for each patient. It will be summarized as a continuous variable.

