9.7. Data Analysis

Detailed methodology for summary and statistical analyses of data collected in this study will be documented in a statistical analysis plan (SAP), which will be dated, filed and maintained by the sponsor. The SAP may modify the plans outlined in the protocol; any major modifications of primary endpoint definitions or their analyses would be reflected in a protocol amendment.

Analyses will be descriptive in nature, as no hypothesis is being tested. Disease staging, comorbidities, demographic, clinical characteristics will be described at the date of diagnosis and/or treatment initiation for patients diagnosed with B-cell ALL R/R or AML. Treatment and clinical information will be assessed up to the most recent data available at the study enrollment. The treatments will be described in sequence according to the chronological order of administration. The duration through the number of cycles will be evaluated. Dose reduction information will also be collected.

Continuous variables will be described as mean and standard deviation (SD), and/or as median, minimum, maximum, interquartile range (IQR, 25th and 75th percentiles).

Categorical variables will be described by simple and cross contingency tabulation, with absolute frequencies and percentages. Missing values will be included in the denominators for the calculation of percentages and missing categories will be presented.

All time-to-event analysis will be described using a Kaplan Meier plot, if appropriate. The following definition and parameter analysis will be considered:

- Follow-up period – considered the time elapsed since B-cell ALL R/R or AML diagnosis until the study enrollment. It will be presented in years.
- Time to next treatment (TTNT) – considered as the time from the start date of the front-line therapy to the start date of a subsequent line of therapy. It will be presented in months.
- Overall survival (OS) – considered as death from any cause from the time of initiation of diagnosis or treatment.^{70,71} The median overall survival (OS) and the % of alive patients in 1, 3- and 5-years follow up of newly diagnosed AML and relapsed/refractory B-cell ALL patients will be assessed.

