- Relapse-free survival (RFS) for newly diagnosed AML patients – considered as measured from the date of achievement of a remission until the date of relapse or death from any cause; patients not known to have relapsed or died at last follow-up are censored on the date they were last examined. Defined only for patients achieving CR, or CRI.

- Event-free survival (EFS) of newly diagnosed AML and relapsed/refractory B-cell ALL patients – considered as the measured from the date of initiation of treatment to the date of primary refractory disease, or relapse from CR, or CRi, or death from any cause; patients not known to have any of these events are censored on the date they were last examined

All computations and generation of tables, listings, graphics, and data for figures will be performed using R® version 3.5.3 or newer version (R Core Team), or a comparable statistical software package.

Medical Dictionary for Regulatory Activities Terminology (MedDRA) version 2.1 (V2.1) or newer version will be used as a standardised medical terminology. Medicinal product names will be codified using World Health Organisation Drug Dictionary (WHODrug), a dictionary maintained and updated by Uppsala Monitoring Centre (UMC).

The resource utilization (eg, number of hospital admissions, hospitalization period, procedures during hospital admissions) will be presented as mean number per patient per year (PPPY). According to the sample distribution, the data will be presented with a standard deviation (SD) or a 95% confidence interval (95% CI), which will be estimated either by Poisson regression or Gama distribution. The PPPY will be calculated as the sum of all event observed in the cohort divided by the total follow-up period (in years) of all patient in the cohort (including those who did not present the event).

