8.1. Study Design

The current study is a retrospective multicenter non-interventional study using real-world data collected from medical records to describe the epidemiology of acute leukemias and treatment patterns among patients diagnosed with B-cell ALL R/R or AML in 4 Latin American countries: Argentina, Brazil, Chile, and Colombia. In addition, as secondary objectives, the study will also describe molecular profile, cytogenetic risk, clinical outcomes, and healthcare resource utilization of treated B-cell ALL R/R and AML patients.

All patients with newly diagnosed AML or with R/R B-cell ALL diagnosed between 01 January 2015 and 31 December 2019 will be included in the study for medical chart abstraction. Data on demographics, clinical characteristics, treatment regimens, among others will be collected. Healthcare resource utilization will be captured to understand the management pattern of both patient's population. All relevant data reported in the medical chart since diagnosis date (index date) until the study enrollment or death, whichever comes earlier, will be assessed.

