8.2. Setting

8.2.1. Study Time Period

For this study, data from patients treated at public or private healthcare facilities in Argentina, Brazil, Chile, Colombia, diagnosed with R/R B-cell ALL or AML between 01 January 2015 and 31 December 2019 will be considered for the analysis.

The eligibility period of 5 years was determined to increase the overall patient representativeness, and to allow ample follow-up to assess survival outcomes.

The study will be conducted in approximately 15 sites distributed across Argentina, Brazil, Chile, and Colombia, and is expected to enroll approximately 700 patients with R/R B-cell ALL and AML in a consecutive matter. To assure the representativeness of each country, the number of sites and the total expected enrolled patients will be limited according to the country, considering the prevalence/incidence of the diseases.

Data collection will occur in a period of up to 12 months following the independent ethics committee (IEC)/ institutional review board (IRB) approval and study set up. Patients will be consecutively enrolled, considering both target population, with no set proportion of AML and R/R B-cell ALL patients to be included in the study. However, it is expected a higher proportion of AML patients in the cohort. The study period will comprise since diagnosis date (index date) until the study enrollment or death, whichever comes earlier.

[figure not shown]

Figure 1. Study time period.

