8.2.3. Follow-up Period and Censoring

Patients will be followed in the cohort from the index date until the end of the study period or the patient's last information available in the databases.

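### SAP 8.7 lets follow-up run on after death to enrollment, contradicting other SAP sections, and the per-patient-per-year (PPPY) formula does not say which follow-up it divides by

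*SAP*

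**What the plan says.** The SAP describes the end of follow-up in several places, and they do not agree.

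- **SAP 8.7, follow-up:** "Follow-up period will be considered the time (in years) elapsed since B-cell ALL R/R or AML diagnosis until the study enrollment". It is then to be summarized as a continuous variable. Protocol 9.7 has the same rule: "considered the time elapsed since B-cell ALL R/R or AML diagnosis until the study enrollment".
- **SAP 8.2.3:** "Patients will be followed in the cohort from the index date until the end of the study period", or to the last information available, without saying which of the two applies first.
- **SAP 8.2.1:** "The study period will comprise since diagnosis date (index date) until the study enrollment or death, whichever comes earlier".
- **SAP 8.1:** chart data "since diagnosis date (index date) until the study enrollment or death, whichever comes earlier, will be assessed".
- **SAP 8.7, PPPY:** "For each resource utilization, the PPPY will be calculated as the sum of all utilizations, divided by the follow up, for each patient". No definition of follow-up is cited. The protocol's pooled version is "divided by the total follow-up period (in years) of all patient in the cohort".
- **SAP 8.3.2 and 8.7.2, item 13:** resource use is observed from diagnosis until loss of follow-up or death.
- **SAP 8.7.1:** the enrolled set includes deceased patients entered under a consent waiver.

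For time to next treatment, SAP 8.7 does write out a complete stop rule: patients without a further line "will be censored at study enrollment, last visit, last contact, or death, whichever comes first".

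**The concern.** Two programmers could follow this SAP faithfully and report different rates. One takes the definition printed in the section that holds the PPPY formula and divides by time to enrollment. The other combines 8.2.3 with 8.2.1 and stops at death. The first gives a deceased patient years of person-time in which no resource use could occur. It does the same for a patient lost to follow-up before enrollment.

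The protocol strengthens the first reading. Its PPPY formula uses the term follow-up period, which its own section 9.7 defines with no stop at death.

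Two outputs are exposed. Healthcare resource use is a stated secondary objective, and in a descriptive study the estimate is the result. The follow-up summary is affected directly: as written, it includes time after death even if PPPY is programmed correctly.

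**Working it through.** The documents give no follow-up time and no PPPY figure, so there is nothing to reproduce. The check has three parts.

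**1. Do the definitions give different values?** They do for anyone who died or was last seen before enrollment. For a patient who dies at time T after diagnosis and is enrolled at time E > T:

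| Source | Follow-up |
|---|---|
| SAP 8.7, Protocol 9.7 | E |
| SAP 8.2.3 read with 8.2.1 | T |
| Resource-use window (item 13) | T |

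**2. Date arithmetic, with no survival model.** Diagnosis falls between 1 January 2015 and 31 December 2019. Data collection is planned for July 2021 to August 2022 (Protocol section 6, which says the dates may change) and is used here as the enrollment window.

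- Shortest E: 31 December 2019 to 1 July 2021 = 548 days / 365.25 = 1.50 years.
- Longest E: 1 January 2015 to 31 August 2022 = 2,799 days / 365.25 = 7.66 years.
- Midpoint: 4.58 years.

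A patient who dies at 1 year has a denominator E/1 = 1.50 to 7.66 times too long. An assumed patient with 3 admissions who dies at 6 months has a true PPPY of 3/0.5 = 6.0. The uncapped rule gives 3/1.50 = 2.0, 3/4.58 = 0.65 or 3/7.66 = 0.39, which is 3 to 15 times too low.

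**3. Cohort illustration.** Assumptions: diagnosis and enrollment dates uniform over their windows, exponential survival with rate λ = ln 2 / median, no loss to follow-up, and a constant rate of use while alive. Let A = min(T, E). If the true rate is 1.00 per year:

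- the pooled denominator is inflated by mean(E)/mean(A), with mean(E) = 4.58 years;
- the SAP's per-patient form reports mean(A/E).

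| Assumed median OS | mean(A), years | mean(E)/mean(A) | mean(A/E) | Times too low | Dead before enrollment |
|---|---|---|---|---|---|
| 36 months | 2.74 | 1.67 | 0.63 | 1.60 | 63% |
| 24 months | 2.21 | 2.07 | 0.52 | 1.94 | 77% |
| 12 months | 1.34 | 3.41 | 0.32 | 3.09 | 93% |

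Sensitivity:

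- With 20% long-term survivors and an overall median of 12 months, mean(A/E) is 0.39, about 2.5 times too low.
- If enrollment ran to 9 December 2022 (the date of SAP version 2.0), mean(E) is 4.72 years and the per-patient factors are 1.62, 1.97 and 3.17.
- Fixing E at 4.58 years and assuming 1-year mortality p, with λ = −ln(1 − p) and mean(A) = (1 − e^(−λE))/λ: p = 30%, 50%, 70% gives mean(A) = 2.26, 1.38, 0.83 years and person-time 2.0, 3.3, 5.5 times too long. The 70% end matches the upper figure in Protocol 7.3, which covers only AML patients aged 65 or older.

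**The case against.** The strongest reply is that the documents, read as a whole, already stop at death. SAP 8.2.3 is the section on follow-up and censoring. It ends follow-up with the study period, which 8.2.1 ends at enrollment or death. SAP 8.1 agrees, as do Protocol 9.1 and 9.2. The data analysis entry in the protocol abstract goes further: it ends data assessment at the earliest of enrollment, last visit, contact date or death, just before it mentions the follow-up period. On this view the 8.7 sentence is only an abbreviation. Section 8.7 and the attached table shells (TLF workbook) were also updated after a test on 20% of the data, so the derivation may be settled in a workbook that could not be read here.

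It can be added that PPPY is reported only if possible, that the outputs listed under item 13 are mostly counts needing no denominator, and that OS, EFS, RFS and TTNT have their own censoring rules.

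Much of this is true, and it limits the point. A bias in PPPY is not established, because one available reading is correct. A patient with no use of a resource has a rate of 0 either way. The survival endpoints are unaffected. But passages that cap the data window or study period do not amend an explicit, uncapped definition of follow-up in the analysis section. They conflict with it. A correct workbook would not remove that conflict, and the follow-up summary is wrong on the plain wording of 8.7.

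**Conclusion.** The point holds and should be fixed. The follow-up rule in SAP 8.7 contradicts SAP 8.1, 8.2.1 and 8.2.3, and it counts time after death for deceased patients. PPPY cites no definition and sits beside the faulty one. If that definition is used, PPPY is too low for every patient who used the resource and died before enrollment.

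Confidence is high for the conflict in the text. The size is illustrative: roughly 1.6 to 3.1 times too low with the per-patient formula, for assumed median OS of 36 to 12 months. It rests on planned dates, exponential survival, constant use while alive and no loss to follow-up. The documents give no median OS for this cohort. The range for a death at 1 year, 1.5 to 7.7 times, needs only the planned dates.

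**What to change.** Change the SAP only:

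1. In 8.7, define follow-up as index date to the earliest of death, last contact or enrollment. The TTNT bullet already has equivalent wording.
2. In the PPPY paragraph, name that definition as the denominator.
3. In 8.2.3, state that the earlier of the two end points applies.

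Record the departure from the follow-up definition in Protocol 9.7. Protocol 9.7 lets the SAP modify the plan and reserves amendments for major changes to primary endpoints, so none is needed. The cost is two or three sentences, a check of the derivation in the TLF workbook and, if it is uncapped there, a small programming change. No new data are required.

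While editing, note that OS, EFS and RFS censor at the latest of several dates. A survivor's follow-up could then be shorter than the OS censoring time. That is a separate matter, but the SAP should say whether it is intended.

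Optional: once person-time stops at death, very short survivors can dominate a per-patient ratio. One admission in 7 days is 365.25/7 = 52 per year. Reporting the protocol's pooled rate as well, with a confidence interval from a count model using log person-years as offset, would guard against this.

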7.3. Treatment for AML and ALL

Among the therapeutic approaches, patients can be selected for an intensive treatment, which consists of either systemic or local (including intrathecal) chemotherapy.³³ Besides chemotherapy, other types of treatment can be recommended according to patient status, including hematopoietic stem cell transplantation (HSCT); investigational products offered in clinical trials and targeted therapy. According to the patient's characteristics, patients should first undergo an induction therapy to achieve complete remission, with a subsequent consolidation therapy in order to achieve a negative minimal residual disease (MRD).

Although advances in the treatment of AML have led to significant improvements in outcomes for younger patients, prognosis in the elderly who account for the majority of new cases remains poor. Even with current treatments, as much as 70% of patients 65 years or older will die of their disease within 1 year of diagnosis.⁴ Except for those with acute promyelocytic leukemia, approximately 50% of patients under 60 years and 90% of patients over 60 years will.³

The main induction therapy for AML changed minimally over the past 40 years and consist of the 7+3 regimen, which combines 7 days of continuous infusion cytarabine with 3 days of anthracycline.^{34,35} The combination of fludarabine, cytarabine, Granulocyte colony stimulating factor (G-CSF) and idarubicin (FLAG-IDA), which was traditionally used for the treatment of relapse, has also been shown to be a reasonable alternative to standard induction regimens and results in similar CR rates and overall survival (OS) with higher rates of CR after a single course.⁴ Nevertheless, the treatment approach for elderly patients with AML are not a consensus. These patients usually have a poor response to the conventional regimens, and in some cases are indicated for supportive care and palliative chemotherapy.

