8.7.2. Descriptive Analysis by Objective

1. Both clinical and demographic characteristics will be described for each newly AML and R/R B-cell ALL patients cohorts and for overall cohort (both novo AML and R/R B-cell ALL). No statistical testing will be carried out for demographic or clinical characteristics. Only descriptive data will be reported (absolute number, frequency, mean \pm standard deviation, median, interquartile range, minimum or maximum).

Demographic characteristics at diagnosis

- Age at diagnosis
- Gender (Female, Male)
- Race/Ethnicity

- County of residence
- Health insurance type.

Clinical data description for newly AML patients at diagnosis

- Comorbidities at newly AML diagnosis;
 - Anxiety
 - Cardiovascular disease
 - Cerebrovascular disease
 - Chronic pulmonary disease
 - Depression
 - Diabetes
 - Dyslipidemia
 - Hypertension
 - Hepatitis B
 - Hepatitis C
 - HIV/AIDS
 - Human cytomegalovirus (HCMV)/herpes
 - Gastrointestinal disease
 - Liver disease
 - Obesity
 - Renal disease
 - Thyroid disease
 - Other
- Family history of hematological malignances;
- Prior exposure to toxic agents;
- Prior exposure to a high dose of radiation;
- Reason for the exposure: therapeutic radiation for other cancers; accidental exposures, or other (description);
- Bleeding history;
- Tobacco consumption habits.
- Eastern Cooperative Oncologic Group (ECOG) performance status result
- Karnofsky performance status (KPS)
- Year of diagnosis

Clinical data description for R/R B-cell ALL patients at diagnosis

- Comorbidities at newly R/R B-cell ALL diagnosis
- Family history of hematological malignances;
- Prior exposure to toxic agents;
- Prior exposure to a high dose of radiation;
- Reason for the exposure: therapeutic radiation for other cancers; accidental exposures, or other (description);
- Bleeding history;
- Tobacco consumption habits.
- ECOG performance status result
- KPS
- Year of diagnosis

2. For each treatment line, treatment pattern will be described for each newly AML and R/R B-cell ALL patients cohorts. No statistical testing will be carried out. Only descriptive data will be reported (absolute number, frequency, mean \pm standard deviation, median, interquartile range, minimum or maximum) for:

Newly AML patients:

Effective Date: 01Feb2022

- Classification of patient for the standard AML therapy;
- Drug regimen prescribed;
- Gemtuzumab, midostaurin or venetoclax associated with the treatment;
- Regimen type;
- Treatment duration;

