- Time to next treatment;
- Total number of cycles;
- Patients that withdraw and reasons for withdrawing
- Dose reduction
- CNS involvement at disease progression
- Radiotherapy
 - Duration, dose, and local of application
- Intrathecal chemotherapy
 - Drug administered intrathecally
- Stem cell transplant (SCT)
 - Laboratory exams for SCT
 - Post-transplant event
- Laboratory exams before and after treatment line

R/R B-cell ALL patients:

- Regimen type
- Drug regimen prescribed
- Treatment duration
- Time to next treatment
- Total number of cycles
- Patients that withdraw and reasons for withdrawing
- CNS involvement at disease progression
- Radiotherapy
 - Duration, dose, and local of application
- Intrathecal chemotherapy
 - Drug administered intrathecally
- Stem cell transplant (SCT)
 - Laboratory exams for SCT
 - Post-transplant event
- Laboratory exams before and after treatment line

Secondary Objective(s)

3. For each treatment line, only descriptive data (absolute number, frequency, mean ± standard deviation, median, interquartile range, minimum or maximum) will be described for cytogenetic and/or molecular testing and immunophenotyping for each newly AML and R/R B-cell ALL patients cohorts:

newly AML and R/R AML

- Molecular test performed
- AML translocation result
- Molecular profile;
- AML WHO classification
 - AML with recurrent genetic abnormalities
 - AML with t(8;21)(q22;q22.1);RUNX1-RUNX1T1
 - AML with inv(16)(p13.1q22) or t(16;16)(p13.1;q22);CBFB-MYH11

- APL with PML-RARA
- AML with t(9;11)(p21.3;q23.3);MLLT3-KMT2A
- AML with t(6;9)(p23;q34.1);DEK-NUP214
- AML with inv(3)(q21.3q26.2) or t(3;3)(q21.3;q26.2); GATA2, MECOM
- AML (megakaryoblastic) with t(1;22)(p13.3;q13.3);RBM15-MKL1
- Provisional entity: AML with BCR-ABL1
- AML with mutated NPM1
- AML with biallelic mutations of CEBPA
- Provisional entity: AML with mutated RUNX1
- AML with myelodysplasia-related changes
- Therapy-related myeloid neoplasms
- AML, NOS
- Immunophenotyping result

newly B-cell ALL and R/R B-cell ALL

- Molecular test performed
- Molecular profile;
- ALL cytogenetic risk classification according to WHO for B-lymphoblastic leukemia/lymphoma
 - B-lymphoblastic leukemia/lymphoma, NOS
 - B-lymphoblastic leukemia/lymphoma with recurrent genetic abnormalities
 - B-lymphoblastic leukemia/lymphoma with t(9;22)(q34.1;q11.2);BCR-ABL1
 - B-lymphoblastic leukemia/lymphoma with t(v;11q23.3);KMT2A rearranged

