8.7.6. Sub-group Analysis

Sub-group analyses will be conducted as stated in the analysis sections. It should be noted that the study was not designed to detect treatment differences within sub-groups. The following sub-groups will be assessed according to the data availability and described within the analysis sections, as appropriate:

Upon availability of data, primary objectives (clinical and demographics characteristics, and treatment patterns) and survival secondary objectives (EFS, OS, RFS) analysis will be stratified by the:

- ECOG
 - 0-1
 - 2-5
- cytogenetic risk

Effective Date: 01Feb2022

- newly AML: favourable, intermediate and poor/adverse
- R/R B-cell ALL: good prognosis, intermediate prognosis, poor prognosis and undetermined prognosis
- country
 - Argentina,
 - Brazil
 - Chile
 - Colombia
- age range
 - \leq 39 years old at diagnosis
 - 40 – 64 years old at diagnosis
 - \geq 65 years old at diagnosis

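### SAP 8.7 censors time to next treatment at death and uses Kaplan-Meier, so the next line looks sooner and more frequent than it was among all treated patients

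*SAP*

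**What the plan says.** SAP 8.7 defines TTNT as "considered as the time from the start date of the front-line therapy to the start date of a subsequent line of therapy" and adds the censoring rule: "Patients without a subsequent line of therapy will be censored at study enrollment, last visit, last contact, or death, whichever comes first". The definition stands under a general instruction: "All time-to-event analysis will be described using Kaplan Meier methods and plots, if appropriate". Protocol 9.7 has the same definition of TTNT but no censoring rule, so censoring at death was introduced in the SAP.

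TTNT is reported under the second primary objective. SAP 8.7.2 item 2 opens with "For each treatment line, treatment pattern will be described for each newly AML and R/R B-cell ALL patients cohorts" and lists "Time to next treatment" for both cohorts. SAP 8.7.6 adds that, where data allow, "primary objectives (clinical and demographics characteristics, and treatment patterns) and survival secondary objectives (EFS, OS, RFS) analysis will be stratified by the" ECOG group, cytogenetic risk, country and age range.

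The other endpoints handle death differently. It is an event for OS and EFS, and for RFS the SAP says: "The RFS will be measured as the treatment end date until next treatment initiation or date of death, whichever comes first". Neither document names a competing-risk method for TTNT.

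**The concern.** Censoring assumes that the patient could still have the event later. That is reasonable for a patient alive at last contact, but not for one who has died. With death censored, the Kaplan-Meier curve describes at best a hypothetical population in which nobody dies before the next line. Even that reading requires death to be independent of starting a next line, which the SAP does not state and which is doubtful in acute leukemia.

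A reader of a real-world treatment-pattern study will take the curve and median as what happened to the treated patients. Read that way, the next line appears sooner and more frequent than it was. The distortion grows with mortality, so it differs between the strata of SAP 8.6-to-8.7 reporting that matter most here: ECOG, cytogenetic risk, country and age. Two strata with the same next-line rate and different mortality give the same curve, although different shares of their patients reach another line.

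**Working it through.** The documents give no TTNT figure to reproduce, so the check compares what the planned method estimates with the cumulative incidence among all treated patients.

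**Inputs**
- Event, censoring rule and estimator: SAP 8.7, as quoted.
- Net 12-month probability of starting a next line, *p*: not in the documents; assumed 20%, 40% and 60%.
- Net 12-month probability of death before a next line, *q*: not in the documents; assumed 10%, 30%, 50% and 70%. The 70% is an upper case. It borrows the Protocol 7.3 statement on AML that "as much as 70% of patients 65 years or older will die of their disease within 1 year of diagnosis", a figure that runs from diagnosis and includes deaths after later lines.
- Constant, independent hazards.

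**Formulas** (hazards per year, *t* in years)
- *a* = −ln(1−*p*), *d* = −ln(1−*q*)
- Planned estimate: 1−KM(*t*) = 1−exp(−*a·t*), which is *p* at 12 months
- True share: CIF(*t*) = *a*/(*a*+*d*) × [1−exp(−(*a*+*d*)*t*)]
- Share who ever start another line (plateau): *a*/(*a*+*d*)
- Kaplan-Meier median in months: 12·ln2/*a*
- Month by which half of all patients have started: −12·ln(1−0.5/plateau)/(*a*+*d*), which exists only if the plateau exceeds 50%

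**Worked case, *p* = 40%, *q* = 30%.** *a* = 0.5108, *d* = 0.3567, sum 0.8675. The plateau is 0.5108/0.8675 = 58.9%. Since exp(−0.8675) = 0.6 × 0.7 = 0.42, CIF at 12 months is 0.589 × 0.58 = 34.2%, against 40% from Kaplan-Meier. The Kaplan-Meier median is 12 × 0.6931/0.5108 = 16.3 months; half of all patients have started at 26.2 months.

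**True share with a next line at 12 months, and excess of 1−KM in percentage points**

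| Net deaths at 12 months | KM 20% | KM 40% | KM 60% |
|---|---|---|---|
| 10% | 19.0% (+1.0) | 38.1% (+1.9) | 57.4% (+2.6) |
| 30% | 16.9% (+3.1) | 34.2% (+5.8) | 51.8% (+8.2) |
| 50% | 14.6% (+5.4) | 29.7% (+10.3) | 45.5% (+14.5) |
| 70% | 11.9% (+8.1) | 24.4% (+15.6) | 38.0% (+22.0) |

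**Median, *p* = 40%**

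| Net deaths at 12 months | KM median | Half of all patients started | Plateau |
|---|---|---|---|
| 10% | 16.3 months | 18.0 months | 83% |
| 30% | 16.3 months | 26.2 months | 59% |
| 50% | 16.3 months | never | 42% |
| 70% | 16.3 months | never | 30% |

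**Strata.** In the *p* = 40% column, strata with 10% and 70% deaths share one Kaplan-Meier curve, but 38% and 24% of their patients have started another line by 12 months.

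**Early deaths.** If deaths cluster early (Weibull shape 0.5, same 30% at 12 months), the excess rises from 3.1/5.8/8.2 to 4.1/8.0/11.5 points.

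**Simulation.** With 700 patients, 300 replicates, uniform administrative censoring at 18 to 90 months and a true Kaplan-Meier median of 9 months, 30% deaths gave mean medians of 9.0 months (Kaplan-Meier) and 11.1 months (Aalen-Johansen), and 12-month shares of 60% and 52%. With 70% deaths the shares were 60% and 38%, and the cumulative incidence never reached 50% in any replicate.

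**Observed times only.** A median of TTNT taken only over patients who started another line errs further in the same direction. With unlimited follow-up it is 12·ln2/(*a*+*d*) = 8.318/0.8675 = 9.6 months in the worked case, against 16.3 from Kaplan-Meier and 26.2 for all patients.

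**The case against.** The best case for the plan has four parts.

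- **A Kaplan-Meier display of TTNT is not certain.** SAP 8.7.2 items 7 to 10 order Kaplan-Meier analyses for EFS, OS and RFS explicitly, whereas item 2 lists TTNT under general descriptive statistics. The general Kaplan-Meier sentence is qualified, and the table shells in SAP 13.1 are not visible. It stands that the planned display cannot be checked. But the qualifier names no alternative, and a censoring rule has a use only in a Kaplan-Meier type of analysis.
- **Mortality is shown elsewhere.** EFS covers both cohorts from treatment start with death as an event, and EFS and OS are stratified by the same factors, so readers would see mortality beside TTNT. This mitigates the problem, but neither endpoint gives the timing of the next line. RFS combines next treatment with death, but only for AML patients in CR or CRi and from treatment end. Counts per line are unaffected, but they carry no timing and do not allow for differing follow-up.
- **The study is descriptive, and TTNT is one item among several rather than a named outcome.** Both are true and limit the weight of the point. In a descriptive study, however, the description is the product.
- **The size is assumed.** It is. With 10% deaths the excess is only 1.0 to 2.6 points, and the contrast of 10% with 70% is an extreme illustration. The direction needs no such assumption.

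**Conclusion.** The concern holds. Under the stated rule, 1 minus Kaplan-Meier is never below the cumulative incidence of a next line, and lies above it once deaths precede next-line starts. The median is correspondingly too early for all treated patients. That is the comparison meant by too soon: the raw median among patients who did start another line is earlier still.

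Under constant, independent hazards the excess at 12 months runs from 1.0 to 22.0 points over the assumed range, and from 3.1 to 8.2 points with 30% deaths. With 50% or more deaths and a 40% net next-line probability, Kaplan-Meier reports a median of 16.3 months although half of the patients never start another line. These sizes depend on rates that the documents do not give. The point is worth correcting before the analysis because TTNT is listed under a primary objective and stratified by factors along which mortality can be expected to differ.

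**What to change.** In SAP 8.7, make death before a next line a competing event for TTNT, and restrict censoring to patients not known to have died, at last contact. The present earliest-of rule has to be reworded accordingly, so that a last visit shortly before a recorded death no longer censors that patient.

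Report the Aalen-Johansen cumulative incidence of next line and of death without a next line, for example at 6, 12 and 24 months with 95% confidence intervals, by cohort and by stratum where numbers allow. In SAP 8.7.2 item 2, label any mean, SD or median of observed TTNT as applying only to patients who started another line, and align the table shells.

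The cost is SAP wording and a standard procedure. The dates are already needed for RFS and EFS. There are two limits: a single median TTNT may not be estimable, and deaths missing from the charts, which SAP 8.8 acknowledges, will leave the incidence of death somewhat understated.
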